## 12.2 Disposition of Subjects

A subject is considered:

- Enrolled if he/she was randomized or if not randomized he/she performed the product trial and he/she confirmed to be willing to use the product.
- Completed Confinement, Completed Day 30, Day 60, Day 90 Visits if he/she did not discontinue until the discharge at Day 6, Day 31, Day 61, and Day 91 respectively.

The number and percent of subjects will be summarized for the following categories: subjects screened, screening failures that tried product, screening failures that did not try product, enrolled subjects, enrolled and not randomized, randomized subjects, completed confinement, completed Day 30 Visit, completed Day 60 Visit, completed Day 90 Visit, completed study, and discontinued (if applicable discontinued subject that never used their allocated products will be identified).

Inclusion and exclusion criteria will be listed as to whether the subjects have met or not met the criteria.

All subjects who fail to complete the study will be categorized by their primary reason for discontinuation and summarized by randomization arm for the FAS. Disposition of subjects and reasons for discontinuation will also be summarized separately. Supportive listings will be provided.

The number and percent of randomized subjects with protocol deviations will be summarized by randomization arm for the PP Set and Safety Population broken down by main deviation category (major/minor), sub-categories and evaluability. Subjects will be counted once per deviation category, and can be counted for more than one deviation category.

The number and percent of randomized subjects included in each analysis population will be summarized by randomization arm for the Safety Population. For subjects excluded from the analysis populations this will be broken down by reason for exclusion. Subjects will be counted once per exclusion, and can be counted for more than one exclusion.

Supportive listing will be provided, including any additional comments for tests that are not performed to be included on the listings of individual data.

The data will be presented in the below outputs:

TFL number	Title
TABLES	
15.2.1.1	Summary of Subject Disposition – All Screened Subjects
15.2.1.2	Summary of Reasons for Discontinuations – FAS

TFL number	Title
15.2.1.3.1	Summary of Protocol Deviations – Safety Population
15.2.1.3.2	Analysis Sets and Reasons for Exclusions from Analyses
LISTINGS	
15.3.1.1	Listing of Inclusion/Exclusion Criteria
15.3.1.8	Listing of Subject Disposition, Randomization and Assignment to Analysis Sets
15.3.1.10	Listing of Protocol Deviations
15.3.2.3	Listing of Subject and Observations Excluded from Analysis Populations
16.1.7	Listing of Randomization Schemes and Codes

### 12.3 Demographics and Other Baseline Characteristics

Demographic and baseline characteristics will be summarized for the Safety Population, FAS and for the PP Set in periods 1-4.

The demographic variables age, sex, race, body weight, height, BMI and waist circumference will be summarized by randomization arm, and by the two stratification factors (sex, and mCC consumption). Other baseline characteristics will also be included in the table.

No inferential analyses will be presented for the demographic and baseline characteristics.

The data will be presented in the below outputs:

TFL number	Title
TABLES	
15.2.1.4.1	Summary of Demographics and Other Baseline Characteristics – Safety Population
15.2.1.4.2	Summary of Demographics and Other Baseline Characteristics – FAS
15.2.1.4.3	Summary of Demographics and Other Baseline Characteristics – PP Set
15.2.1.4.3.1	Summary of Demographics and Other Baseline Characteristics by Sex – PP Set
15.2.1.4.3.2	Summary of Demographics and Other Baseline Characteristics by Cigarette Consumption – PP Set
LISTINGS	
15.3.1.7	Listing of Demographics

#### 12.3.1 Current Cigarette Brand and Smoking Characteristics

The following smoking characteristics at Admission (Day -2) will be summarized and listed as specified in Section 12.3 “Demographics and Other Baseline Characteristics”: number of mCCs smoked (categorized as 10-19 cig/day and >19 cig/day). The summaries will be presented for the Safety Population, FAS and PP Set.

Current mCC brand(s) smoked by the subject and recorded at Screening will be summarized for the FAS. Only brands used by at least 4 subjects will be tabulated. An “other” category will contain all the brands used by less than 4 subjects. All the data at Screening and Admission (Day -2) will be listed by randomization arm and study day.

Smoking history, including whether subjects have smoked for at least the last three consecutive years and the subject’s mCCs consumption during the previous 4 weeks will be listed by randomization arm at Screening and Admission (Day -2) where applicable.

Data will be listed and summarized as presented in the below outputs:

TFL number	Title
TABLES	
15.2.1.4.1	Summary of Demographics and Other Baseline Characteristics – Safety Population
15.2.1.4.2	Summary of Demographics and Other Baseline Characteristics – FAS
15.2.1.4.3	Summary of Demographics and Other Baseline Characteristics – PP Set
15.2.1.4.3.1	Summary of Demographics and Other Baseline Characteristics by Sex – PP Set
15.2.1.4.3.2	Summary of Demographics and Other Baseline Characteristics by Cigarette Consumption – PP Set
15.2.1.5	Summary of Current Cigarette Brands – Safety Population
LISTINGS	
15.3.1.2	Listing of Current Cigarette Brands
15.3.1.3	Listing of Smoking History

### 12.3.2 Socio-Economic Status Questionnaire

subject answers will be listed.. The number and percentage of subjects in each of the socio-economic status gradings (see Section 7.3.1 “Socio-Economic Status Questionnaire”) will also be summarized as reported in Section 12.3 ‘Demographics and Other Baseline Characteristics”, and presented in listings as shown below:

TFL number	Title
TABLES	
15.2.1.4.1	Summary of Demographics and Other Baseline Characteristics – Safety Population
15.2.1.4.2	Summary of Demographics and Other Baseline Characteristics – FAS
15.2.1.4.3	Summary of Demographics and Other Baseline Characteristics – PP Set
15.2.1.4.3.1	Summary of Demographics and Other Baseline Characteristics by Sex – PP Set
15.2.1.4.3.2	Summary of Demographics and Other Baseline Characteristics by

TFL number	Title
	Cigarette Consumption – PP Set
LISTINGS	
15.3.1.11	Listing of Socio-Economic Questionnaire Results

### 12.3.3 Medical History and Concomitant Diseases

Medical history is defined as any condition that started and ended prior to Screening. Concomitant disease is defined as any condition that was ongoing at Screening.

Medical history and concomitant disease will be coded using MedDRA version 16.0 or later and listed separately by randomization arm, System Organ Class (SOC) and Preferred Term (PT) within SOC.

Medical History and concomitant disease will be summarized by randomization arm, SOC and PT for the Safety population.

The data will be presented in the below outputs:

TFL number	Title
TABLES	
15.2.1.6	Summary of Medical History – Safety Population
15.2.1.7	Summary of Concomitant Diseases – Safety Population
LISTINGS	
15.3.1.9	Listing of Medical History and Concomitant Diseases

### 12.3.4 Other Data

Other data collected at Screening and/or Admission will be listed by randomization arm. These data are as follows:

- Cotinine urine test
- Urine pregnancy test
- Chest x-ray
- Urine drug screen
- Serology
- Alcohol breath test
- Prior medication
- Willingness to use THS 2.2 Menthol products.
- Product preference question

Prior Medication will be listed as described in Section 12.6.4.4.1 “Prior and Concomitant Medication”.

Product preference will be collected at Admission (Day -2) and states the product which the subject prefers to be randomized to (THS 2.2 Menthol, mCC, SA or No preference).

Data will be summarized by randomization arms along with Baseline characteristics. Willingness and ability to use the product will be included in the disposition summary table for all screened subjects.

The data will be presented in the below outputs:

TFL number	Title
TABLES	
15.2.1.1	Summary of Subject Disposition – All Screened Subjects
LISTINGS	
15.3.1.4	Listing of Product test and Willingness to Use the Product
15.3.1.5	Listing of Product Preference
15.3.1.6	Listing of Safety Laboratory Entry Criteria
15.3.6.4	Listing of Prior and Concomitant Medication

## **12.4 Measurements of Product Compliance**

From Day -2 onwards during the confinement period, each mCC will be dispensed to the subjects one by one. Subjects in the THS 2.2 Menthol arm will be provided by the site study collaborators with Menthol Tobacco Sticks from Day 1 to Day 5 stick by stick. One mCC/Menthol Tobacco Stick will be allowed at a time.

Levels of CO in exhaled breath will be measured in the SA arm to ensure that the subjects have not smoked any cigarettes. This will serve as a compliance tool starting from Day 2, because of possible carry over effect. These data (continuous and categorical) will be summarized and listed by product use category (Table 25) in the SA arm.

During the ambulatory period, subjects in the 3 study arms will capture, from the time of Discharge on Day 6 to Day 90, the number of product used (e.g., menthol and non-menthol CC, Menthol Tobacco Sticks, or any other tobacco /nicotine-containing products including NRT) on a daily basis in the product use electronic diary. The product use electronic diary will serve as a compliance tool in the 3 arms. On Day 6, the compliance to the product will be ensured using both the accountability log (from 06:30 AM to time of discharge) and the product use electronic diary (filled from the time of Discharge on Day 6 to Day 90).

The data will be presented in the below outputs:

TFL number	Title
TABLES	
15.2.5.1	Summary of Compliance as Measured by Exhaled CO (ppm) During Confinement Period - FAS in the SA Arm
LISTINGS	
15.2.5.2	Summary Of Compliance by Period and Overall - FAS
15.3.3.2	Listing of Bood, Plasma, Serum, and Exhaled Air Biomarkers
15.3.2.1.1	Listing of Product Usage (CC) During Confinement Period

TFL number	Title
15.3.2.1.2	Listing of Product Usage (THSm2.2) During Confinement Period
15.3.2.1.3	Listing of Product Usage During Ambulatory Period

## 12.5 Extent of Exposure (Product Consumption)

Details of the product test prior to enrollment and of product use after randomization will be listed and summarized. During the confinement period the daily usage as recorded in the log will be summarized by randomization arm.

The maximum and average daily usage of the assigned product and non-assigned product will be summarized over the whole ambulatory period, as recorded by the subject, and for each of the periods 2 to 4 (see section 10.2 “Per Protocol Set”).

All summaries will be produced for the Safety Population, and for the PP Set at periods 1 to 4. Summaries of data in Ambulatory will also be repeated for the FAS, if the population differs from the Safety population by more than 10%.

In addition the number and percentage of subjects falling into each product use category (see Section 6.3.3.1 “Dual-use”) during the ambulatory period will be presented.

The average product use data will also be presented by randomized product and by product use categorization (see Section 6.3.3.1 “Dual-use”).

The data will be presented in the below outputs:

TFL number	Title
TABLES	
15.2.2.1.1	Summary of Daily Product Use in Confinement Period – FAS
15.2.2.1.2	Summary of Daily Product Use in Confinement Period – PP Set
15.2.2.2	Summary of Maximum Daily Product Use in Ambulatory Period – FAS
15.2.2.3.1	Summary of Average Daily Product Use in Ambulatory Period – FAS
15.2.2.3.2	Summary of Average Daily Product Use in Ambulatory Period – PP Set
15.2.2.4	Summary of Product Use by Product Use Category in Ambulatory Period – FAS

TFL number	Title
15.2.2.5.1	Summary of Average Daily Product Use by Product Use Category in Ambulatory Period – FAS
15.2.2.5.2	Summary of Average Daily Product Use by Product Use Category in Ambulatory Period – PP Set
LISTINGS	
15.3.2.1.1	Listing of Product Usage (CC) During Confinement Period
15.3.2.1.2	Listing of Product Usage (THSm2.2) During Confinement Period
15.3.2.1.3	Listing of Product Usage During Ambulatory Period
15.3.2.2	Listing of THS 2.2 Menthol Device Details

## 12.6 Planned Statistical Analyses

For all statistical analysis data from all arms, THS 2.2 Menthol, mCC and SA will be included in all models as appropriate.

### 12.6.1 Primary Analyses

#### 12.6.1.1 Analysis of Biomarkers of Exposure for Primary Endpoints

The BoExp (COHb in blood and urinary concentrations of MHBMA, 3-HPMA, S-PMA and Total NNAL) used for the primary analysis will be summarized as detailed in Section 12.1.3 “Descriptive Statistics”. The listing of the COHb data will have a flag for whether a subject’s COHb was <2%.

The baseline is as defined in Section 12.1.4 “Definitions for Statistical Data Analysis”.

The primary endpoints will be log-transformed (basee) prior to analysis. The analysis will compare the evening COHb level (20:00-21:30 PM) on Day 5; and urinary concentrations of MHBMA, 3-HPMA and S-PMA adjusted for creatinine on Day 5 and urinary concentrations of Total NNAL adjusted for creatinine on Day 90 Visit between the THS 2.2 Menthol and mCC arms for the PP Set. An analysis of covariance (ANCOVA) (Snedecor and Cochran 1982) model will be used with terms for the log-transformed baseline value, sex, average daily mCC consumption over the last 4 weeks as reported during screening and randomization arm.

The SAS code to be used for the THS 2.2 Menthol and mCC data is shown below:

```
Proc glm data=_data_;
Class randomization_arm sex cigarette_cons;
Model log_biomarker = log_baseline sex cigarette_cons
randomization_arm;
Lsmean randomization_arm / pdiff =control('mCC') alpha=0.05 cl;
Run;
```

The least squares (LS) means and estimate of the difference and the 95% CI will be back-transformed. The geometric LS means for each randomization arm along with the ratio

(THS 2.2 Menthol : mCC), two-sided 95% CI and one-sided p-value will be presented in the tables. THS 2.2 menthol : mCC effects will be graphed in a forest plot.

All figures, summaries and analyses will be performed on the PP Set. Additional descriptive statistics will be provided within the secondary analysis.

The data will be presented in the below outputs:

TFL number	Title
FIGURES	
15.1.1.1	Forest Plot of Statistical Analysis of Biomarkers of Exposure on Day 5 and Day 90 – PP Set
15.1.1.2	Biomarkers of Exposure Geometric Mean and 95% CI – PP Set
TABLES	
15.2.3.1.1	Analysis of COHb, MHBMA, 3-HPMA, S-PMA and Total NNAL on Day 5/90 Visit for THS 2.2 Menthol versus mCC for the Primary Objective – PP Set
15.2.4.1.1	Descriptive Statistics of Blood COHb (%) – PP Set
15.2.4.1.1.1	Descriptive Statistics of Blood COHb (%) by Sex – PP Set
15.2.4.1.1.2	Descriptive Statistics of Blood COHb (%) by Cigarette Consumption – PP Set
15.2.4.2.1	Descriptive Statistics of MHBMA in 24-hour Urine Collection – PP Set
15.2.4.2.1.1	Descriptive Statistics of MHBMA Urinary Concentration Adjusted for Creatinine (units) in 24-hour Urine Collection by Sex – PP Set
15.2.4.2.1.2	Descriptive Statistics of MHBMA Urinary Concentration Adjusted for Creatinine (units) in 24-hour Urine Collection by Cigarette Consumption – PP Set
15.2.4.3.1	Descriptive Statistics of 3-HPMA in 24-hour Urine Collection – PP Set
15.2.4.3.1.1	Descriptive Statistics of 3-HPMA Urinary Concentration Adjusted for Creatinine (units) in 24-hour Urine Collection by Sex – PP Set
15.2.4.3.1.2	Descriptive Statistics of 3-HPMA Urinary Concentration Adjusted for Creatinine (units) in 24-hour Urine Collection by Cigarette Consumption – PP Set
15.2.4.4.1	Descriptive Statistics of S-PMA in 24-hour Urine Collection – PP Set
15.2.4.4.1.1	Descriptive Statistics of S-PMA Urinary Concentration Adjusted for Creatinine (units) in 24-hour Urine Collection by Sex – PP Set
15.2.4.4.1.2	Descriptive Statistics of S-PMA Urinary Concentration Adjusted for Creatinine (units) in 24-hour Urine Collection by Cigarette Consumption – PP Set

TFL number	Title
15.2.4.5.1	Descriptive Statistics of Total NNAL in 24-hour Urine Collection – PP Set
15.2.4.5.1.1	Descriptive Statistics of Total NNAL Urinary Concentration Adjusted for Creatinine (units) in 24-hour Urine Collection by Sex – PP Set
15.2.4.5.1.2	Descriptive Statistics of Total NNAL Urinary Concentration Adjusted for Creatinine (units) in 24-hour Urine Collection by Cigarette Consumption – PP Set
LISTINGS	
15.3.3.1	Listing of Urinary Biomarkers
15.3.3.2	Listing of Bood, Plasma, Serum, and Exhaled Air Biomarkers

### 12.6.1.2 Confirmatory Analysis

The hypothesis to be tested is that the geometric mean level of the BoExp for THS 2.2 Menthol is lower relative to mCC and will be as described in Section 12.6.1.1 "Analysis of Biomarkers of Exposure for Primary Endpoints".

### 12.6.1.3 Sensitivity Analysis

As a sensitivity analysis, the ANCOVA model described in Section 12.6.1.1 "Analysis of Biomarkers of Exposure for Primary Endpoints" will be repeated for the PP Set at Day 5 and Day 90 data by means of a mixed model approach, without the LOCF data imputation described in Section 12.1.5 "Handling of Dropouts or Missing Data (including outside the limits of quantification)". Any data outside of the allowed time window (see Table 23: Assessment Windows) on Days 5 and 90 will be excluded from the analysis.

The SAS code to be used for the THS 2.2 Menthol and mCC data is shown below:

```
Proc mixed data=_data_;
  Class randomization_arm sex cigarette_cons;
  Model log_biomarker = log_baseline sex cigarette_cons
  randomization_arm;
  Lsmean randomization_arm / pdiff =control('mCC') alpha=0.05 cl;
  Run;
```

An additional sensitivity analysis will be produced for the primary analysis, summaries and graphs of the COHb, MHBMA, 3-HPMA, S-PMA and Total NNAL will be repeated for the compliant population for THS 2.2 Menthol vs mCC. The analysis will use the same model as described in Section 12.6.1.1 "Analysis of Biomarkers of Exposure for Primary Endpoints"

The data will be presented in the below outputs:

TFL number	Title
FIGURES	
15.1.1.3	Biomarkers of Exposure Geometric Mean and 95% CI – Compliant Population
TABLES	
15.2.3.1.2	Sensitivity Analysis of COHb, MHBMA, 3-HPMA, S-PMA and Total NNAL on Day 5/90 Visit for THS 2.2 Menthol versus mCC for the Primary Objective using Mixed Model – PP Set
15.2.3.1.3	Sensitivity Analysis of COHb, MHBMA, 3-HPMA, S-PMA and Total NNAL on Day 5/90 Visit for THS 2.2 Menthol versus mCC for the Primary Objective – Compliant Population
15.2.4.1.3	Descriptive Statistics of Blood COHb (%) – Compliant Population
15.2.4.2.3	Descriptive Statistics of MHBMA in 24-hour Urine Collection – Compliant Population
15.2.4.3.3	Descriptive Statistics of 3-HPMA in 24-hour Urine Collection – Compliant Population
15.2.4.4.3	Descriptive Statistics of S-PMA in 24-hour Urine Collection – Compliant Population
15.2.4.5.3	Descriptive Statistics of Total NNAL in 24-hour Urine Collection – Compliant Population

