#### 12.1.5 Handling of Dropouts or Missing Data (including outside the limits of quantification)

For laboratory parameters:

- Values below the lower limit of quantification (LLOQ) will be imputed using LLOQ/2. For values above the upper limit of quantification (ULOQ), the ULOQ will be imputed.
- The number of values below LLOQ or above ULOQ will be presented in each summary table. If 50% or more data are below LLOQ or above ULOQ, only the number (%) of value below LLOQ or above ULOQ will be reported in the summaries, together with minimum and maximum of the observed values.
- Missing data at Baseline will not be imputed.

For BoExp:

- A last observation carried forward (LOCF) approach will be implemented to replace all missing data with the last available data for each parameter being assessed.
- For parameters assessed at several timepoints during a visit, the last available data at the timepoint being assessed collected at previous study visit will be used in the analyses. For example, if on Day 5, the evening assessment (20:00-23:00) is missing for COHb, the evening assessment from Day 4 will be used for analysis regardless whether other COHb assessments are available at Day 5.

For daily product use data in safety summaries:

- Product use categories will be defined based on percentage of THS 2.2 Menthol use calculated by averaging non missing consumption data over the entire ambulatory time interval.

For daily product use data in non-safety analyses and summaries:

- If at least 75% of the daily product use assessments over a period are available, with no more than 7-days of consecutive missing data:
  - Product use categories will be defined based on percentage of THS 2.2 use calculated by averaging non missing consumption data over the analysis interval.
  - Compliance to randomized product will be defined based on the available product use data.
- If less than 75% of the daily product use assessments over a period are available, or product use data is missing over a period of more than 7 consecutive days:
  - Product use categories will be defined based on percentage of THS 2.2 use calculated by considering the missing product use data as the CC use reported at Baseline.
  - Compliance to randomized product will be defined by considering the missing product use data as the CC use reported at Baseline.

For MNWS, QSU-brief, and MCEQ questionnaire data:

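### The SAP's 'mixed model' check on LOCF is an observed-case ANCOVA: it uses no earlier visits and is mixed up with the removal of out-of-window data

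*SAP*

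**What the plan says.** SAP 12.6.1.1 sets out the primary analysis. "An analysis of covariance (ANCOVA) (Snedecor and Cochran 1982) model will be used with terms for the log-transformed baseline value", together with sex, cigarette consumption and randomization arm, in the PP Set; the code opens with "Proc glm data=_data". SAP 12.1.5 governs missing biomarkers of exposure: "A last observation carried forward (LOCF) approach will be implemented to replace all missing data with the last available data".

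SAP 12.6.1.3 then repeats this ANCOVA on the Day 5 and Day 90 data "by means of a mixed model approach, without the LOCF data imputation". The same paragraph makes a second change: "Any data outside of the allowed time window (see Table 23: Assessment Windows) on Days 5 and 90 will be excluded from the analysis". The code opens with "Proc mixed data=_data" and continues with "Class randomization_arm sex cigarette_cons" and "Model log_biomarker = log_baseline sex cigarette_cons", followed by the arm term. SAP 12.6.2.1 extends the analysis to the remaining biomarkers. The titles of Tables 15.2.3.1.2 and 15.2.3.6 both say that a mixed model was used.

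**The concern.** A reader of those table titles will expect a longitudinal model that keeps subjects with partial follow-up and relies on a missing-at-random assumption. The code cannot do that, because it names neither subject nor visit. Each subject contributes one record, and a subject without the Day 5 or Day 90 value contributes none. The Day 1-4 and Day 30 and Day 60 values are collected but not used.

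This matters because it is the only planned analysis of the primary endpoints without LOCF. The other sensitivity analysis, on the compliant population, reuses the primary model. LOCF is a doubtful rule for Total NNAL in particular, since Protocol 4.2 gives it a half-life of 10 to 15 days and levels in switchers are still falling at the early visits. Removing out-of-window data in the same run also means that two things change at once.

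**Working it through.** **1. The plan's own figures.** The plan attaches no number to this analysis. Its stated power at the 50% margin (SAP Table 20) was reproduced to confirm the log-scale inputs. The formulas are SD = sqrt(ln(1 + CV²)) and margin = ln(0.50 / mean ratio), one-sided 2.5%, with 80:40 subjects for the Day 5 markers and 40:40 for NNAL.

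- NNAL (mean ratio 0.30, CV 0.60): SD = sqrt(ln 1.36) = 0.5545; margin = ln(0.50/0.30) = 0.511; SE = 0.5545 × sqrt(1/40 + 1/40) = 0.124; power 0.9846.
- YVD-CS01-EU assumptions: COHb 0.9582 × 3-HPMA 0.9999 × MHBMA 1.0 × S-PMA 1.0 × NNAL 0.9846 = 0.943 (stated 94%).
- ZRHX-EX-01 assumptions: COHb 0.9973 × NNAL 0.9846, the others 1.0, gives 0.982 (stated 98%).

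**2. Are the two analyses the same model?** Without RANDOM or REPEATED, PROC MIXED assumes independent errors with one common variance, which is the PROC GLM model. Both were fitted to one simulated data set, by least squares and by REML:

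| Records | Method | Log-ratio | SE | df | 95% CI |
|---|---|---|---|---|---|
| All 80 | GLM | -1.08617 | 0.095295 | 75 | -1.27601 to -0.89633 |
| All 80 | MIXED as coded | -1.08617 | 0.095295 | 75 | -1.27601 to -0.89633 |
| 64 observed | GLM | -1.04111 | 0.110998 | 59 | -1.26322 to -0.81900 |
| 64 observed | MIXED as coded | -1.04111 | 0.110998 | 59 | -1.26322 to -0.81900 |

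Any difference from the primary result therefore comes from which records are used, not from the procedure.

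**3. How far off is a carried NNAL value in the THS arm?** THS use starts on Day 1 (Protocol 4.1). The fraction of the initial excess that remains is 2^(-elapsed days / half-life):

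| Value | Elapsed days | Half-life 10 days | Half-life 15 days |
|---|---|---|---|
| Day 30 | 29 | 0.13 | 0.26 |
| Day 60 | 59 | 0.017 | 0.065 |
| Day 90 | 89 | 0.002 | 0.016 |

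**4. Can the planned comparison detect this?** The documents give no missing-data rate, so 5% to 20% missing at random in both arms was assumed. Other assumptions: 40:40, CV 0.60, within-subject correlation 0.7, steady-state ratio 0.30. The true Day 90 ratio is then 0.301 to 0.311.

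- LOCF from Day 5: 0.317 to 0.380.
- LOCF from Day 30: 0.306 to 0.338.
- LOCF from Day 60: 0.302 to 0.317.
- Observed-case ANCOVA: 0.300 to 0.312.

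So it can.

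**5. Missingness that depends on an earlier value.** The true ratio was set to 0.30 at Day 60 and Day 90. About 20% of mCC Day 90 values were missing, more often after a high Day 60 value, and the THS arm was complete. LOCF gave 0.289, the observed-case ANCOVA 0.305, and a genuine mixed model on both visits (subject random intercept, visit interactions) 0.297. All three used the same simulated data, so the ordering is more informative than the third decimal. LOCF falls below 0.30 because mCC values selected for being high are carried forward.

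**The case against.** The strongest reply is that the SAP promises no more than it delivers. Its written aim is to repeat the ANCOVA without LOCF, and the code does so. Nothing in the SAP says that intermediate visits will be used or that missingness will be assumed random. SAP 12.6.2.2 calls the same code for an ANCOVA at each timepoint separately. This stands. A reader might infer that the analysis fails to test LOCF, or that a promised longitudinal model was left out; the documents support neither reading, and step 4 contradicts the first.

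A second reply is that other rules limit the damage. Under SAP 12.1.5, if fewer than 75% of diary days are available or more than 7 consecutive days are missing, the missing days count as baseline cigarette use. With at least 10 a day required at entry, that breaches the limits in Table 21 (more than 2 in a day, or more than 0.5 a day on average). Most early THS dropouts should therefore leave the Day 90 PP Set before LOCF matters. A Day 30 value also reaches Day 90 only if both later visits are missing. Both arguments stand for the THS arm. They do not cover the mCC arm: Table 21 defines ambulatory product non-compliance only for the THS and SA arms, and Table 22 lists a missing assessment or visit as minor, so mCC subjects can remain on carried values.

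A third reply is that compliance is judged by period, so a model across periods needs a rule on who contributes. That is correct, and the fix supplies one.

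**Conclusion.** The analysis is mislabelled and weaker than its title suggests. It is the primary ANCOVA on observed, in-window records. It can show an LOCF effect, but it leaves selective missingness unaddressed and cannot separate LOCF from the window exclusion.

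The effect on the result is probably small. A THS value that is too high moves the ratio towards 1, against the product's claim. In the mCC scenario LOCF erred in the product's favour, but the three methods differed by at most 0.016 (0.305 - 0.289). A reader might infer that LOCF could produce a false success; no scenario examined came near that, the largest ratio being 0.380 against 0.50.

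The equivalence of the two procedures rests on no assumption. The sizes rest on the protocol's half-life, the plan's NNAL ratio and CV, an assumed within-subject correlation of 0.7 and assumed missing rates of up to 20%. The change should be made, but the primary conclusion does not depend on it.

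**What to change.** Replace the code in SAP 12.6.1.3 with a repeated-measures model on the log scale. Terms: arm, visit, arm-by-visit, log baseline, baseline-by-visit, sex and consumption stratum, with REPEATED visit / subject and an unstructured covariance. Use Days 1-5 for the Day 5 markers and Days 30, 60 and 90 for Total NNAL. Restrict it to the PP Set of the period that contains the endpoint (period 1 or period 4), state which visits contribute, and report the Day 5 or Day 90 contrast. Run the out-of-window exclusion as a separate analysis.

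If the present code is kept, call it 'observed-case ANCOVA' in the text and in the titles of Tables 15.2.3.1.2 and 15.2.3.6.

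The cost is slightly more programming and one written rule on visits; no new data are needed. Several later sections (for example 12.6.2.2, 12.6.2.4 and 12.6.3.2.2) borrow the 12.6.1.3 code for by-timepoint ANCOVAs, so those cross-references would have to point to 12.6.1.1 instead.
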